### Suitability of Subject Population

The intended study population is adult subjects  $\geq$  18 to 65 years of age with NSV. Subjects with documented clinical diagnosis of NSV and no segmental or localized vitiligo are eligible for this study. At study entry, eligible subjects must have at least 0.5 F-VASI and at least 5 T-VASI. Criteria relating to safety have been selected to allow subjects to be safely enrolled and treated with upadacitinib based on the current knowledge of this drug.

### Selection of Doses in the Study

This study is designed as a dose-ranging study to evaluate upadacitinib doses of 6 mg, 11 mg, and 22 mg QD in adult subjects with vitiligo. These doses were selected to provide comprehensive dose-ranging information in patients with vitiligo through evaluation of upadacitinib doses that have not been studied in other upadacitinib indications (e.g., RA, PsA, AS, and AD).

Patients with vitiligo generally present with a clinically (and biologically) different disease profile compared to previously studied indications for upadacitinib. Although vitiligo significantly impairs QoL, it is generally considered an asymptomatic dermatosis (some patients may suffer from skin irritation/itching), and is usually associated with lower comorbidities, minimal background and concomitant therapies, and less heterogeneous signs and symptoms of the disease. Hence, the upadacitinib dose(s) that may provide optimal benefit risk in patients with vitiligo are yet to be determined and may occur at dose levels that have not been previously explored for other indications.

Upadacitinib 15 mg QD and 30 mg QD doses showed significant clinical benefit for treatment of subjects with RA, PsA, AS, and AD in Phase 3 studies, with an added clinical benefit of 30 mg compared to 15 mg for some (e.g., AD) but not all (e.g., RA, PsA) indications.

Two case studies have reported partial re-pigmentation of vitiligo white patches after administration of tofacitinib, a pan JAK-inhibitor, at a 5 mg twice a day dose together with narrowband UV-B therapy. Although the observed response in these 2 case studies was achieved with a combination of tofacitinib and phototherapy, the findings suggest that JAK inhibition with dose levels comparable to efficacious doses in RA and PsA populations may provide clinical efficacy in patients with vitiligo. Whether lower or higher doses could provide similar or higher efficacy, respectively, remains unclear and requires more data from adequate dose-ranging studies in patients with vitiligo.

Hence, upadacitinib doses of 11 mg and 22 mg have been selected to allow evaluation of upadacitinib exposure levels below and above the 15 mg dose, respectively, that have not been evaluated in other indications. The proposed 11 mg and 22 mg doses are expected to provide upadacitinib exposures that partially overlap with those achieved with the 15 mg dose, but at the same time provide enough separation between the doses to enable adequate characterization of the dose/exposure-response relationship. The 6 mg dose was selected to ensure characterization of the minimally efficacious dose in the vitiligo patient population.

## 5 STUDY ACTIVITIES

### 5.1 Eligibility Criteria

---

Subjects must meet all of the following criteria in order to be included in the study. Anything other than a positive response to the questions below will result in exclusion from study participation.

#### Consent

- 1. Subject must be able to understand and willing to adhere to all protocol requirements and voluntarily **sign and date an informed consent**, approved by an Independent Ethics Committee (IEC)/Institutional Review Board (IRB), prior to the initiation of any screening or study-specific procedures.

#### Demographics

- 2. Adult (**male or female**)  $\geq 18$  to 65 years of age.

#### Disease/Condition Activity

- 3. Documented clinical diagnosis of NSV.
- 4. At Screening and Baseline visits, subjects must have  $\geq 0.5$  F-VASI AND  $\geq 5$  T-VASI.
- 5. No segmental or localized vitiligo.

#### Laboratory Assessments

- 6. **Laboratory values** meeting the following criteria within the Screening Period prior to the first dose of study drug:

- Serum aspartate transaminase (AST)  $\leq 2 \times$  upper limit of normal (ULN);
- Serum alanine transaminase (ALT)  $\leq 2 \times$  ULN;
- Estimated glomerular filtration rate  $\geq 30 \text{ mL/min}/1.73 \text{ m}^2$  by simplified 4-variable Modification of Diet in Renal Disease (MDRD) formula;
- Total WBC count  $\geq 2,500/\mu\text{L}$ ;
- Absolute neutrophil count (ANC)  $\geq 1,200/\mu\text{L}$ ;
- Platelet count  $\geq 100,000/\mu\text{L}$ ;
- Absolute lymphocyte count (ALC)  $\geq 750/\mu\text{L}$ ;
- Hemoglobin  $\geq 9 \text{ g/dL}$ .

## Subject History

- ✓ 7. Subjects are judged to be in good health as determined by the Principal Investigator, based upon the results of medical history, laboratory profile, physical examination, chest x-ray (CXR), and a 12-lead electrocardiogram (ECG) performed during Screening.
- ✓ 8. Subjects must not have a history of clinically significant (per investigator judgment) drug or alcohol abuse within the last 6 months. *(Note: Do not perform urine drug screen at Baseline Visit).*
- ✓ 9. Subjects must have no current or past history of the following:
  - Two or more episodes of herpes zoster, or one or more episodes of disseminated herpes zoster;
  - One or more episodes of disseminated herpes simplex (including eczema herpeticum/Kaposi varicelliform eruption);
  - Human immunodeficiency virus (HIV) infection, defined as confirmed positive anti-HIV antibody (HIV Ab) test;
  - Active tuberculosis (TB) or meet TB exclusionary parameters (specific requirements for TB testing are provided in the operations manual);
  - Positive result of beta-D-glucan (screening for pneumocystis jirovecii infection) or 2 consecutive indeterminate results of beta-D-glucan during the Screening Period (for subjects in Japan only);
  - Active infection(s) requiring treatment with intravenous anti-infectives within 30 days, or oral/intramuscular (IM) anti-infectives within 14 days prior to the Baseline Visit;
  - Chronic recurring infection and/or active viral infection that, based on the investigator's clinical assessment, makes the subject an unsuitable candidate for the study;
  - Confirmed COVID-19: The Baseline Visit must be at least 14 days from onset of signs/symptoms or positive SARS-CoV-2 test; symptomatic subjects must have recovered, defined as resolution of fever without use of antipyretics and improvement in symptoms;

- Suspected COVID-19: Subjects with signs/symptoms suggestive of COVID-19, known exposure, or high risk behavior should undergo molecular (e.g., polymerase chain reaction [PCR]) testing to rule out SARS-CoV-2 infection or must be asymptomatic for 14 days from a potential exposure.
- ✓ 10. Subjects must not have evidence of:
  - Hepatitis B virus (HBV): hepatitis B surface antigen positive (+) test or detectable HBV DNA PCR qualitative test for subjects who are hepatitis B core antibody (HBc Ab) positive (+)(and for hepatitis B surface antibody [HBs Ab] positive [+] subjects where mandated by local requirements);
  - Hepatitis C virus (HCV): detectable HCV RNA in any subject with anti-HCV Ab.
- ✓ 11. Subjects must not have any of the following medical diseases or disorders:
  - Recent (within past 6 months) cerebrovascular accident, myocardial infarction, coronary stenting, and aorto-coronary bypass surgery;
  - History of an organ transplant which requires continued immunosuppression;
  - History of GI perforation (other than due to appendicitis or mechanical injury), diverticulitis, or significantly increased risk for GI perforation per investigator judgment;
  - Conditions that could interfere with drug absorption including but not limited to short bowel syndrome or gastric bypass surgery; subjects with a history of gastric banding/segmentation are not excluded;
  - History of malignancy except for successfully treated NMSC or localized carcinoma in situ of the cervix;
  - Uncontrolled thyroid disease;
  - Other skin conditions that would interfere with evaluation of vitiligo;
  - > 33% leukotrichia on the face or > 33% leukotrichia on the body (including face).
- ✓ 12. There must be no reason the investigator believes that the subject is an unsuitable candidate to participate in the study, receive study drug, or would be placed at risk by participating in the study.

## Contraception

- ✓ 13. For all females of child-bearing potential: must not have a positive serum pregnancy test at the Screening Visit and must have a negative urine pregnancy test at Baseline prior to the first dose of study drug (local practices may require serum pregnancy testing at Baseline). Subjects with a borderline serum pregnancy test at Screening must have absence of clinical suspicion of pregnancy or other pathological causes of borderline results and a serum pregnancy test  $\geq$  3 days later to document continued lack of a positive result (unless prohibited by local requirements).

- ✓ 14. Female subjects of childbearing potential must practice at least 1 protocol-specified method of birth control that is effective from Study Day 1 through at least 30 days after the last dose of study drug (local practices may require 2 methods of birth control) (refer to Section 5.2 for more details on contraception). Female subjects of non-childbearing potential do not need to use birth control.
- ✓ 15. Female must not be **pregnant, or breastfeeding, and is not considering becoming pregnant or donating eggs** during the study and for 30 days after the last dose of study drug.

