#### Females of Childbearing Potential

Review and document pregnancy avoidance recommendations with females of childbearing potential.

Females of childbearing potential must avoid pregnancy while taking study drug and for at least 30 days after the last dose of study drug. Females must commit to one of the following methods of highly effective birth control:

- Combined (estrogen- and progestogen-containing) hormonal birth control (oral, intravaginal, transdermal, injectable) associated with inhibition of ovulation initiated at least 30 days prior to study Baseline Day 1.
- Progestogen-only hormonal birth control (oral, injectable, implantable) associated with inhibition of ovulation initiated at least 30 days prior to study Baseline Day 1.
- Bilateral tubal occlusion/ligation (can be via hysteroscopy, provided a hysterosalpingogram confirms success of the procedure) (For Japan: only bilateral tubal ligation).
- Intrauterine device (IUD).
- Intrauterine hormone-releasing system (IUS).
- Vasectomized sexual partner (the partner has received medical confirmation of the surgical success of the vasectomy and is the sole sexual partner of the trial subject).
- Practice true abstinence (unless not acceptable per local practices), defined as: refraining from heterosexual intercourse when this is in line with the preferred and usual lifestyle of the subject (periodic abstinence [e.g., calendar, ovulation, symptothermal, post-ovulation methods] and withdrawal are not acceptable).

If required per local practices, females of childbearing potential must commit to using 2 methods of contraception (either 2 highly effective methods or 1 highly effective method combined with 1 effective method). Effective methods of birth control are the following:

- Progestogen-only oral hormonal contraception, where inhibition of ovulation is not the primary mode of action, initiated at least 30 days prior to Baseline Day 1.
- Male or female condom with or without spermicide.
- Cap, diaphragm, or sponge with spermicide.
- A combination of male condom with a cap, diaphragm, or sponge with spermicide (double barrier method).

Contraception recommendations related to use of concomitant therapies prescribed per standard of care should be based on the local label.

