## Pregnancy

While not an AE, pregnancy in a study subject must be reported to AbbVie within 1 calendar day after the site becomes aware of the pregnancy. If a pregnancy occurs in a study subject, information regarding the pregnancy and the outcome will be collected.

Female subjects should avoid pregnancy throughout the course of the study, starting with the Screening Visit through 30 days after the last study drug administration. Results of a positive pregnancy test or confirmation of a pregnancy will be assessed starting with the Screening Visit through the final study visit.

Subjects who become pregnant during the study must be discontinued from study drug treatment (Protocol Section 5.5).

The pregnancy outcome of an elective or spontaneous abortion, stillbirth, or congenital anomaly is considered an SAE and must be reported to AbbVie within 24 hours of the site becoming aware of the event.

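### Women who start an IUD or IUS shortly before Day 1 have no required contraception during Screening, a small safety gap that two wording edits would narrow

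*Protocol*

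**What the plan says.** Three places in the protocol set a start point.

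- **Section 6.1, Pregnancy** (advisory, no method named): "Female subjects should avoid pregnancy throughout the course of the study, starting with the Screening Visit".
- **Section 5.1, criterion 14** (binding, on method): "Female subjects of childbearing potential must practice at least 1 protocol-specified method of birth control that is effective from Study Day 1".
- **Section 5.2, Females of Childbearing Potential** (binding, on avoidance): women "must avoid pregnancy while taking study drug and for at least 30 days after the last dose".

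Section 5.2 then lists the accepted methods. Combined and progestogen-only hormonal methods are described as "associated with inhibition of ovulation initiated at least 30 days prior to study Baseline Day 1". The IUD and the IUS are listed with no lead-in. Tubal occlusion or ligation, a vasectomized partner and true abstinence also have no lead-in in days. Hysteroscopic occlusion and vasectomy need confirmed success, however, and abstinence must already be the woman's usual practice.

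For testing, criterion 13 rules out a positive serum test at Screening and says that these women "must have a negative urine pregnancy test at Baseline prior to the first dose of study drug". Serum testing at Baseline happens only where local practice requires it. Appendix D schedules further urine tests at Week 2, Week 4 and every 4 weeks after that. Section 2.2 describes the drug as teratogenic in animals and gives that as the reason pregnancy has to be avoided.

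**The concern.** The rule on method begins on the day dosing begins. For hormonal users the lead-in carries protection back into Screening. For a woman who has an IUD or IUS placed just before or on Day 1, nothing binding requires any method in the preceding weeks. Screening can last 35 days, so the serum test may be that old at the first dose. The only later test required of every such woman before dosing is the urine test, and a urine test needs some days after conception to turn positive. She could have a negative Baseline result and start a teratogenic drug while in very early pregnancy. What is at stake is fetal exposure in a few women, not the trial's inference.

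**Working it through.** The plan gives no figure to reproduce. The check is a day count.

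**Inputs from the protocol**
- Screening runs from Day -35 to Day -1, and there is no Day 0 (Appendix D).
- Urine tests: Baseline (Day 1), Week 2 (Day 15) and Week 4 (Day 29). The Period 1 visit window is read as plus or minus 3 days from a partly broken table, giving Days 12 to 18 and Days 26 to 32.
- Dosing is once daily from Day 1 (Section 5.7).
- Hormonal methods are started by Day -30 (Section 5.2).

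**Assumptions not in the documents**
- A urine test turns positive L whole days after conception; 7 to 18 is shown.
- The method is fully effective from Day -m, with m = 0 meaning Day 1.
- Pregnancy is not separately excluded when a device is placed.

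**Formula.** A conception on Day -k is k + d - 1 days old on Day d, so a test on Day d misses it if k + d - 1 < L. Only days with k > m are unprotected. The number of unprotected conception days missed on Day d is therefore max(0, L - d - m). At Baseline (d = 1) this is max(0, L - 1 - m). For example, L = 14 with a device effective from Day -5 gives 14 - 1 - 5 = 8 days.

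**Hormonal users.** A method started on Day -30 that takes t days to work has m = 30 - t. The Baseline window is 0 only if 30 - t is at least L - 1, that is, t is at most 30 - (L - 1).

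| L (days) | Missed at Baseline, m = 0 | Window is 0 if effective by | Still missed, Week 2 test on Day 12, m = 0 | Still missed, Week 2 test on Day 15, m = 0 | Longest hormonal onset t giving a 0 window |
|---|---|---|---|---|---|
| 7 | 6 | Day -6 | 0 | 0 | 24 days |
| 10 | 9 | Day -9 | 0 | 0 | 21 days |
| 12 | 11 | Day -11 | 0 | 0 | 19 days |
| 13 | 12 | Day -12 | 1 | 0 | 18 days |
| 14 | 13 | Day -13 | 2 | 0 | 17 days |
| 16 | 15 | Day -15 | 4 | 1 | 15 days |
| 18 | 17 | Day -17 | 6 | 3 | 13 days |

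A Week 2 test on Day 18 misses none (18 - 18 = 0 at the longest lag), and a Week 4 test on Day 26 or later misses none.

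**Exposure before detection.** Doses taken before a test on Day d number d - 1.
- Week 2: 14 doses on Day 15, with a range of 11 (Day 12) to 17 (Day 18).
- Week 4: 28 doses on Day 29, with a range of 25 (Day 26) to 31 (Day 32).

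Even at L = 18 and m = 0, a Day 15 test leaves 3 of the 17 missed days undetected and a Day 12 test leaves 6 of 17. Most are found at Week 2.

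**The case against.** The strongest reply is that the controls are layered and the residue is thin. Criterion 15 bars women who are pregnant or considering pregnancy during the study, and Section 4.1 counts Screening as part of the study. Criterion 13 requires two tests, with serum at Baseline where local practice requires it. Criterion 12 lets the investigator exclude a woman who would be put at risk. Appendix D has sites review pregnancy avoidance, apparently from Screening. Study drug stops if pregnancy is found (Section 5.5). Harm needs a chain: no contraception in Screening, a device placed late, pregnancy not excluded at placement, conception within the test lag and no local serum test. The operations manual (Appendix F) is not among the documents and may tell sites more.

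Most of this stands, and it limits the weight of the point. It does not close the gap. Criterion 15 addresses status and intent, so an unintended and undetected conception passes it. Criterion 12 is general discretion. The Week 2 test shortens exposure but cannot prevent it. None of the text available requires a method before dosing.

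A reader might infer that Section 6.1 contradicts criterion 14. It does not: one is advice on avoiding pregnancy, the other a rule on method, and both can be followed together.

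**Conclusion.** The point holds as a low-cost safety improvement. A woman who starts a method without a lead-in (mainly an IUD or IUS) shortly before Day 1 has no required method before it takes effect. The conception window missed at Baseline is max(0, L - 1 - m) days: 0 for established users, and at most 6 days (L = 7) to 17 days (L = 18) when protection starts only on Day 1. These figures rest on the assumed lag and on pregnancy not being excluded at placement.

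Three stronger readings are not supported.
- The 6 to 17 days do not apply to every IUD or IUS user; they are the worst case.
- Hormonal users are not safe unconditionally. Section 5.2 fixes when the method is started, not when it works, so a 0 window needs onset within 30 - (L - 1) days.
- Detection only at Week 4 is not the usual outcome. With a Week 2 test on Day 12 it needs a lag of at least 13 days (one conception day at 13, two at 14). With a test on Day 15 it needs at least 16.

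Few women are likely to be affected, but the number cannot be derived from the documents.

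**What to change.** Make two edits in the next protocol amendment.

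1. **Criterion 14.** Require the protocol-specified method to be effective no later than Study Day 1, keeping the existing end point. Add: *From the Screening Visit until that method is effective, the subject must either abstain from heterosexual intercourse or use one of the barrier methods listed as effective in Section 5.2. The 30-day lead-in for hormonal methods is unchanged.* State that this interim abstinence is separate from the true abstinence method, which Section 5.2 defines as "refraining from heterosexual intercourse when this is in line with the preferred and usual lifestyle of the subject".
2. **Section 5.2.** Add the Screening Visit as the start of the binding obligation to avoid pregnancy, ahead of the period on study drug.

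Section 6.1 and Appendix D need no change. The cost is amendment and consent wording with ethics committee approval (Section 8.1), and a short interim precaution for women who start a method without a lead-in during Screening. No visit, test or analysis is added.

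The edits reduce the gap but may not remove it. If the Screening Visit is S days before Day 1 and the interim measure works fully, max(0, L - 1 - S) days remain, ignoring the Screening serum test. At L = 18 that is 10 days for S = 7, 3 days for S = 14 and 0 for S of 17 or more. At L = 7 it is 0 for S of 6 or more.

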#### Prior and Concomitant Medications and Therapies

- ✓ 16. Subjects must not have previously been treated with any topical or systemic JAK inhibitor.
- ✓ 17. Subjects must not have previously been treated with any permanent skin bleaching agents to treat vitiligo.
- ✓ 18. Subjects must not have been treated with any investigational drug of chemical or biologic nature within a minimum of 30 days or 5 half-lives (whichever is longer) prior to the first dose of study drug or is currently enrolled in another interventional clinical study or was previously enrolled in this study.
- ✓ 19. Subjects who have had prior exposure to immunomodulatory biologic therapy, for any indications, must have discontinued the biologic therapy prior to the first dose of study drug. Recommended washout periods are specified below. If not specified below, biologic therapies must be discontinued at least 5 times the mean terminal elimination half-life of a drug or 3 months prior to Baseline, whichever is longer.
  - $\geq 4$  weeks for etanercept;
  - $\geq 8$  weeks for adalimumab, infliximab, certolizumab, golimumab, abatacept, tocilizumab, and ixekizumab;
  - $\geq 16$  weeks for secukinumab;
  - $\geq 12$  weeks for ustekinumab.
- ✓ 20. Subjects must not have been treated with any systemic vitiligo therapy (e.g., methotrexate [MTX], mycophenolate mofetil, corticosteroids) or supplemental vitiligo therapy (antioxidants/vitamins/herbal medicine/traditional Chinese medicine) within a minimum of 30 days prior to the first dose of study drug.
- ✓ 21. Subjects must not have been treated with any topical vitiligo therapy including permanent and temporary tattoos within a minimum of 30 days prior to the first dose of study drug. (Note: Camouflage and makeup may be used).
- ✓ 22. Subjects must not have been treated with any phototherapy, including excimer (or other forms of laser therapy), within a minimum of 12 weeks prior to the first dose of study drug.

- ✓ 23. Subjects must have no systemic use of known strong cytochrome P450 3A (CYP3A) inhibitors from Screening through the end of study drug administration or strong CYP3A inducers 30 days prior to study drug administration through the end of study drug administration (refer to [Table 1](#) in Section [5.3](#) for examples of commonly used strong CYP3A inhibitors and inducers). Subjects may not use herbal therapies or other traditional medicines with unknown effects on CYP3A from Screening through the end of study drug administration.
- ✓ 24. Subjects must not have received a live vaccine within 28 days (or longer if required locally) prior to the first dose of study drug, or have expected need of live vaccination during study participation including at least 30 days (or longer if required locally) after the last dose of study drug.
- ✓ 25. Subjects must not have a history of an allergic reaction or significant sensitivity to constituents of the study drug (and its excipients) and/or other products in the same class.

